In this study, we will continue to test the efficacy of the device on individuals with stroke in their home environment. Efficacy will be evaluated based on the change in gait coordination as well as other gait and mobility parameters including gait speed, balance, and fall risk. This study will also integrate motion sensor technology in order to obtain real-time data, e.g. gait analysis. We predict that the device will continue to demonstrate changes to interlimb coordination of gait as well as improvement in gait and mobility parameters.

[figure not shown]

Figure 1: Picture of device – note that wheels are designed such that downward force (i.e. from standing) will cause them to rotate and move the shoe backwards, relative to the ground. (bottom) The motion of the device from heel contact until toe off of walking. The device was measured to have a smooth horizontal backward motion of approximately 6-8" (15-20 cm).

1. Background information, description of existing research, and information that is already known

In the United States, nearly 800,000 people suffer a stroke each year, and approximately two-thirds of these individuals survive⁸. Many people suffer from significant and long-lasting motor deficits that require rehabilitation. One such motor deficit that frequently occurs is hemiparesis, or a weakness on one side. Among ischemic stroke survivors over 65 years old, half had some degrees of hemiparesis persisting six months post-stroke.⁹ Lower limb hemiparesis leads to asymmetric walking patterns, called hemiparetic gait.^{10,11} Specific characteristics of hemiparetic gait include asymmetries in temporal (e.g. swing time and double-support time)^{10,12} and spatial (e.g. step length)¹³ measures of interlimb coordination. That is, the timing and placement of the feet are not equal on the two sides.

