The goal of this study is to test the efficacy, safety, and feasibility of the iStride™ device to correct gait asymmetry and improve gait parameters including gait speed and balance in individuals with stroke. The study will be structured around subjects walking on the device with their gait recorded and analyzed before and after device usage. The study design is within-subjects where each individual's gait will be compared before, during, and after the treatment period. The study will be conducted on chronic stroke patients in a home-based setting. The treatment will last at least four weeks with an initial visit prior to the start of treatment and several follow-up tests targeted at one month, three months, six months and twelve months post-treatment, in order to measure retention. A subset of the home study patients may be asked to continue treatment with variations in frequency and duration. In addition, several customization factors, specifically to the wheel size, may be tested in order to determine if patients plateau at any point during their rehabilitation. This is important in order to determine the most beneficial prescription for patients while using the device. Additionally, in order to assess muscle activation and response, a subset of these subjects may be asked to visit an alternate clinic site for EMG testing pre and post-treatment.

The home-based treatment will consist of at least twelve treatment sessions performed over a minimum of four weeks with a gait evaluation pretest and initial fitting of the shoe the week before. Gait evaluations will be performed the week before the first treatment and periodically during treatment (no more than once per week). Follow-up tests will be targeted at one week, one, three, six, and twelve months after the final treatment session.

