During the treatment, the licensed physical therapist will determine, based on eligibility, if the participant can use the device with their caregiver providing supervision (without the presence of the physical therapist each session). To promote continued safety, the caregiver would be required to participate in a treatment session on the device and would need to demonstrate adequate knowledge of device usage as well as how to walk with the participant safely. The therapist would have weekly or monthly follow-up visits to monitor continued safety, protocol adherence, and progress. Additionally, the participant may communicate some or all sessions with a licensed therapist via telemedicine video conferencing using the 9zest digital health rehab platform (<https://9zest.com>). This communication may be used to enhance communication with the physical therapist. This telemedicine modality is verified HIPPA compliant.

A cross over component may also be employed, in which an equal number of treatment sessions will be duplicated without the device, before or after the device treatment. In a study of this type, the patients will have an equal number of sessions of treatment without the device, in the setting and in the way the treatment will occur with the device. (e.g. at home with caregiver supervision and a physical therapist intermittently following-up).

The treatment sessions will consist of approximately 30 minutes of treatment on the device. The treatment duration will be divided into up to six shorter bouts of walking to allow rest breaks between walking sessions, if needed. Additional breaks will be given as needed upon subject request. Based on the pre-treatment gait analysis, we will evaluate all parameters (such as walking speed, double limb support, stance time, etc) and make a decision to maximize their recovery in regard to which foot the device will be placed on. The device will encourage them to take larger steps with that foot. The total treatment sessions will be no longer than one hour.

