A study physician or an advanced registered nurse practitioner (ARNP), rehabilitation clinician with knowledge, or subject's physician will perform medical screening or sufficient review of a medical record for the subjects that will participate in the proposed studies. This screen will be used to determine if the potential subjects had one or more cerebral strokes without other medical conditions (e.g., other neurological, orthopedic, etc.) that would affect or explain the subjects' walking or limb movement. Clinical assessments may consist of vision, proprioception, gait analysis and cognitive screening. The 10 Meter Walk Test, Timed Up and Go Test²⁴, Berg Balance Scale, and Functional Gait Assessment tests will be performed to assess changes in subjects' gait velocity, aerobic capacity, and risk of falls, respectively, before, during, and following treatment. Additionally, several psychosocial outcomes will be tested.

To measure gait, Veristride motion sensors will be incorporated. These sensors, along with additional sensors will be used during all treatment sessions creating a complete library of data while using the device during treatment. This data will be analyzed with existing algorithms to measure gait parameters as well as assess changes that may occur as a result of iStride™ device usage. For the subjects in this study who perform treatment with caregiver supervision, these sensors will allow us to verify that the subject completed the treatment as specified. A fit bit device may also be used in this study, in order to track compliance, record telemetry-related data, as well as provide an overall collection of steps per patient.

Our main analysis will be to compare the amount of learning (i.e. deviations from symmetry post-adaptation) to normal baseline symmetry. This will be done using a repeated measures ANOVA to compare baseline gait symmetry at the start of the experiment to post-adaptation at the end of the experiment and on the follow-up assessments. We will quantify the amount of adaptation and the change in gait asymmetry by comparing the magnitude of step length and double support differences during baseline, at the beginning of treatment, during treatment, and after treatment. During a symmetric gait, step lengths on each side are the same; during an asymmetric gait, step lengths are different. These measures are standard accepted measures for measuring gait asymmetries.

4. Sample size

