The risks for this study are slightly higher than regular walking over ground and include the possibility of falling. The risk can be compared to walking on high-heeled shoes. To minimize this risk, subjects will be screened for appropriateness of trial participation by licensed physical therapists. For subjects who may be permitted to use this device with caregiver supervision, thorough training of all caregivers will be performed and in-person or video conferencing follow-up by the physical therapist will occur as deemed necessary by the therapist. Subjects determined unable to walk safely on the device by any clinician using the device under these conditions or any reason at any time will not be allowed to continue or start the study. As such, the combined risks associated with this study are minimal.

For this home-based study, steps are taken to ensure safety. We will use a licensed physical therapist to train all caregivers to provide the appropriate level of assistance the patient needs to safely ambulate. If the patient is not able to ambulate safely on the device with caregiver supervision or the caregiver does not demonstrate the ability to safely supervise, the subject will not be allowed participation in the study. The subject will be able to call the physical therapist to discuss their progress and/or any concerns throughout the home-based treatment, at any time. To ensure a proper safety evaluation and assessment of one's home environment, the participant and their caregiver, as well as the physical therapist, must acknowledge the following within their home: proper lighting, safe hallway entrances, and removal of throw rugs and cords. Patient and caregiver will receive fall prevention education including education on the risk of falling, certain safety issues (see above), and mobility restriction. For example, the device is not to be used on stairs. In addition to fall prevention, education will be provided on movement patterns and position changes. The safety provisions will be discussed and assessed prior to the start of treatment by a licensed physical therapist.

8. The potential benefits to subjects

There is potential for subjects to improve their gait patterns, gait speed, and balance which is our hypothesis regarding this method. It may not change their gait, so there may be no benefit to subjects.

9. Human subject considerations

a. Description of the informed consent process

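### A before-after change cannot be credited to the device itself, because a new supervised walking programme starts with it and the no-device comparison is optional

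*Combined protocol and SAP*

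**What the plan says.** The introduction to the combined protocol and SAP says that "we will continue to test the efficacy of the device on individuals with stroke in their home environment". Section 2 gives as the ultimate objective to show that the device can make gait symmetric and improve speed and balance. Section 3 again puts efficacy of the device first, ahead of safety and feasibility.

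The evidence to which the plan commits is before-after. Section 3 states: "The study design is within-subjects where each individual's gait will be compared before, during, and after the treatment period". On the main analysis it says: "This will be done using a repeated measures ANOVA to compare baseline gait symmetry at the start of the experiment to post-adaptation", with the follow-up assessments included. Section 4 sizes the study for a t-test of pre-treatment against post-treatment data.

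On what participants receive, Section 3 says: "The home-based treatment will consist of at least twelve treatment sessions performed over a minimum of four weeks", and "The treatment sessions will consist of approximately 30 minutes of treatment on the device". It adds weekly or monthly therapist follow-up for caregiver-supervised participants, possible video contact, and gait evaluations before, during and after treatment. Section 7 adds that "education will be provided on movement patterns and position changes". Section 5 requires that participants are not in physical therapy at entry and are at least 6 months past their stroke.

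The no-device comparison is conditional: "A cross over component may also be employed, in which an equal number of treatment sessions will be duplicated without the device". Section 3 allows those sessions to come before or after the device sessions.

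**The concern.** The aim is a causal statement about one component, the device. The committed comparison measures everything that changes between baseline and the later assessments. Several things change at once: the device is worn, regular supervised walking begins in people who were not in therapy, contact with a therapist begins, and the same tests are performed again. The repeated measures ANOVA has a time effect and no device-versus-no-device term, so it cannot divide the change among these.

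If the device added nothing and the programme produced ordinary gains, the plan as written would lead to a report of device efficacy. The optional crossover, which would match the sessions in setting and manner but omit the device, is the comparison that bears on the device. No efficacy statement in the plan depends on it.

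**Working it through.** **1. What the study was sized for.** Section 4 gives an effect size of 0.68 on step length difference and 18 subjects. It does not state the significance level, sidedness or power. Assuming a paired t-test at two-sided 5% with 80% power:

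- Normal approximation: n = ((1.960 + 0.842) / 0.68)² = 16.97, so 17.
- Exact noncentral t: n = 19. Power at n = 18 is 77.6%.

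The planned 18 lies between these, so it is consistent with a pre-post test. Nothing in Section 4 sizes a device-versus-no-device contrast.

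**2. What comes with the device.** At least 12 sessions × about 30 minutes = at least about 360 minutes of supervised walking. This is scheduled time on the device; Section 3 allows it to be split into shorter bouts with rests.

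**3. What a before-after test does if the device has no effect.** Let d be the standardised mean change produced by practice, contact and retesting alone. The documents give no value, so d is an assumed range. With n = 18 and 17 degrees of freedom, the two-sided 5% critical value is 2.110 and the noncentrality is d × √18.

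| Assumed non-device gain d | d × √18 | Probability of a significant result |
|---|---|---|
| 0 | 0 | 5.0% |
| 0.2 | 0.85 | 12.6% |
| 0.3 | 1.27 | 22.5% |
| 0.5 | 2.12 | 51.6% |

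**4. Whether the optional crossover would settle it at 18 subjects.** Let f be the share of 0.68 that is due to the device, and ρ the correlation between a subject's changes in the two blocks. Both are assumed, with no carry-over. The standardised contrast is 0.68 × f / √(2(1 − ρ)).

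| f | ρ | Standardised contrast | Power at n = 18 |
|---|---|---|---|
| 1 | 0.5 | 0.680 | 77.6% |
| 1 | 0 | 0.481 | 48.6% |
| 0.5 | 0.5 | 0.340 | 27.5% |
| 0.5 | 0 | 0.240 | 16.1% |

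Only if the whole of 0.68 belongs to the device and ρ is at least 0.5 does the contrast keep the power of the pre-post test.

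**The case against.** The best defence is that the design suits much of what the study is for. The introduction and Section 2 also ask whether outcomes and safety hold up when caregivers supervise and therapists visit intermittently. Section 3 adds feasibility, and Section 1 describes the work as groundwork for later studies. A single arm can serve those aims, and the plan labels its design openly. That stands. It does not cover the efficacy aim. Section 2 names earlier split-belt and device results as points of reference, but no analysis against them is specified.

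The eligibility criteria also help. Enrolment at least 6 months after stroke makes spontaneous recovery less likely, and excluding current physical therapy reduces outside co-treatment. Neither removes practice, contact or retest effects. Those effects are most plausible for speed and balance; the documents do not show that ordinary walking shifts step-length or double-support asymmetry. The device's proposed mechanism makes a symmetry effect credible, but the main analysis does not test it against practice.

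Two stronger readings are tempting and go beyond the text. A reader might infer that the treatment sessions themselves deliver gait coaching and movement education. Section 3 describes caregiver supervision, and therapist visits to monitor safety, adherence and progress. Section 7 places the education within safety instruction and gives no timing for it, so it may precede or follow the baseline test. A reader might also take the phrase "analyzed with existing algorithms to measure gait parameters as well as assess changes that may occur as a result of" as a causal claim for the main result; it concerns the sensor data.

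**Conclusion.** The point holds for the efficacy claim. As committed, a significant baseline-to-post or follow-up change supports a statement about the device together with the supervised home walking programme, and not about the device alone. This follows from the comparison chosen and does not depend on any particular size of non-device effect.

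The rejection rates of 12.6%, 22.5% and 51.6% illustrate the logic only. A reader might take them as this trial's false-positive rate. The documents do not support that, because the gains of 0.2 to 0.5 SD, the two-sided 5% level and the absence of a device effect are all assumed. Nor do the documents show that the device is ineffective.

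A reader might also infer that any completed crossover would justify a device claim. As described it would not. Section 3 leaves the order open and gives no washout or analysis, Section 4 gives no sizing for it, and the plan itself measures retention to twelve months, so carry-over is a real possibility.

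**What to change.** In the introduction and Sections 2 and 3, including the main-analysis paragraph and the sentence on sensor data:

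- Define the baseline-to-post and baseline-to-follow-up change as the effect of the device plus the supervised home walking programme, and state that it will not be reported as an effect of the device alone.
- Allow a device-specific statement only from a device-versus-no-device contrast whose order, carry-over handling and analysis are written down before the data are seen. Report it with its confidence interval and note that 18 subjects were not chosen to power it.
- If that contrast is not run, report programme-level change only.

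The safety, feasibility and caregiver-supervision aims stay as they are. The rewording needs no added participants, visits or staff. Its downside is a more modest efficacy claim. Specifying the contrast takes some planning, and only if the sponsor wants to speak about the device itself.

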Preliminary studies with three healthy test subjects showed statistical data that indicated that the minimum number of subjects for this study is 18.⁴ We powered the t-test between pre-treatment and post-treatment data. We calculated an effect size of 0.68 for step length difference, resulting in an estimated sample size of 18 subjects. The preliminary test with healthy subjects was approved under the Einstein Healthcare Network IRB HN4365, and other preliminary tests with healthy subjects were conducted under USF IRB Pro00001858.

We have no reason to think that women and men will differ in their abilities on any of these tasks. As such, we expect to enroll approximately the same number of men and women.

5. Inclusion and exclusion criteria

We will recruit individuals with stroke for this study. If eligible and willing, individuals that participated in our previous home study may be allowed continued participation. Since the focus of this project is to ultimately use this device to help stroke survivors, we will recruit both young adults and older adults.

Inclusion criteria includes:

- 1) Age 21-80
- 2) One or more cerebral strokes, but all strokes on same side
- 3) Stroke occurred at least 6 months prior to enrollment
- 4) Gait asymmetry, but able to walk independently with or without a cane
- 5) Not currently receiving physical therapy
- 6) No evidence of severe cognitive impairment that would interfere with understanding the instructions
- 7) No evidence of one-sided neglect, affecting ambulation
- 8) At least 25 feet of walking space (does not need to be a straight line)
- 9) Weight does not exceed 275lbs

Exclusion criteria includes:

- 1) Uncontrolled seizures
- 2) Metal implants (stents, clips, pacemaker)
- 3) Pregnancy
- 4) History of a neurological disorder other than stroke (Parkinson's, MS)
- 5) Chronic Obstructive Pulmonary Disease
- 6) Uncontrolled blood pressure
- 7) Head injury in the past 90 days
- 8) Myocardial infarction within the last 180 days
- 9) Cannot rely on a rolling walker for ambulation
- 10) Severe Ataxia
- 11) Previously diagnosed vestibular ear issues

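### The main comparison rests on a single pretest; averaging it with a device-off walk at session 1 would gain precision at little cost

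*Combined protocol and SAP*

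**What the plan says.** Section 3 (study design) schedules one evaluation before treatment, "with a gait evaluation pretest and initial fitting of the shoe the week before". The schedule is then: "Gait evaluations will be performed the week before the first treatment and periodically during treatment (no more than once per week". Follow-up tests come after the last session.

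The main analysis, at the end of section 3, is a repeated measures ANOVA. It sets gait symmetry at the start of the experiment against the end of the experiment and the follow-ups. The same paragraph says that the magnitudes of the step length and double support differences will be compared "during baseline, at the beginning of treatment, during treatment, and after treatment". Baseline and the start of treatment are thus separate occasions, but the text does not say whether the device is on or off at the second. No averaging of pre-treatment values is described.

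The pretest also guides the choice of foot for the device: "Based on the pre-treatment gait analysis, we will evaluate all parameters". Motion sensors "will be used during all treatment sessions creating a complete library of data while using the device during treatment".

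Section 4 gives the sample size: "We powered the t-test between pre-treatment and post-treatment data" and "We calculated an effect size of 0.68 for step length difference, resulting in an estimated sample size of 18 subjects".

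**The concern.** Each participant is their own control. A no-device phase is only optional and may come after the device phase, so the pretest is the one pre-treatment reference that is certain to exist. If a participant walks unusually well or badly that day, the whole deviation passes into the change score. With about 18 people the study has little room for avoidable noise, and section 9e removes non-completers without any allowance for this in section 4.

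A second device-off measurement before treatment would reduce that noise. It would also give a rough view of how far the measures move between two tests before any treatment session. The visit and the sensors are already planned.

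**Working it through.** **Inputs.** From section 4: paired pre/post t-test, effect 0.68, n = 18. Assumed, because not stated: two-sided alpha 0.05, 80% target power, and 0.68 meaning mean change divided by SD of change. Also assumed: a share f of the change variance V is visit-to-visit noise, equal at each visit. No test-retest SD is given, so f is varied from 0 to 1.

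**1. The plan's own figure.** The normal approximation gives n = ((1.960 + 0.842)/0.68)² = 16.97, so 17. The exact noncentral t calculation gives 19. The stated 18 lies between them. Exact power at n = 18 is 77.6%.

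**2. Effect of averaging two baselines.** Let e be the error variance of one visit and τ² the variance of true response. With one pretest V = 2e + τ², so f = 2e/V. With the mean of two pre-treatment values the variance is e/2 + e + τ² = V − e/2 = V(1 − f/4). The standardised effect becomes 0.68/√(1 − f/4).

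| f | SD ratio √(1 − f/4) | Effect | Power, n = 18 | n for 80% |
|---|---|---|---|---|
| 0 | 1.000 | 0.680 | 77.6% | 19 |
| 0.25 | 0.968 | 0.702 | 80.2% | 18 |
| 0.50 | 0.935 | 0.727 | 82.8% | 17 |
| 0.75 | 0.901 | 0.754 | 85.4% | 16 |
| 1 | 0.866 | 0.785 | 88.1% | 15 |

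**3. Correlated errors.** If the errors of the two pre-treatment visits correlate at ρ, the variance is V[1 − f/2 + (f/2)(1 + ρ)/2]. At ρ = 0.5, power is 80.2% for f = 0.5 and 82.8% for f = 1.

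**4. Fewer completers.** With 15 completers (an assumption), power is 68.8% with one pretest, and 74.5% (f = 0.5) or 80.7% (f = 1) with two.

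**5. What the change from pretest to session 1 could show.** Its SD is √(2e) = √f × SD of change. The 95% half-width at n = 18 is 2.110 × √f/√18, which is 0.35 SD of change at f = 0.5 and 0.50 at f = 1. That is 52% to 73% of the planned 0.68.

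**6. Regression to the mean, tested by how asymmetry is scored.** In simulations with no treatment effect, no entry cut-off, the side fixed by the pretest and test-retest correlation 0.7 to 0.9:

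- *Scored as a magnitude*, as section 3 words it: spurious change 0.00. Choosing a foot excludes nobody and does not alter a magnitude.
- *Scored as a signed value relative to the side chosen at the pretest*: 0.11 to 0.33 SD of change, for a true mean asymmetry of 0 or 1 SD. For a mean of 0 the range is 0.18 to 0.33. Averaging brings it to 0.10 to 0.18, and session 1 alone to about zero. In raw units averaging halves the bias (0.24 to 0.12 at correlation 0.7; 0.08 to 0.04 at 0.9).

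A pretest entry cut-off would be a separate route. The approximate bias is i√((1 − r)/2), where i is the selection intensity. With r = 0.9 and the most asymmetric 70% enrolled (i = 0.50) it is 0.11. With r = 0.8 and the top 50% (i = 0.80) it is 0.25. Neither the cut-off nor these correlations is in the documents.

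**The case against.** One baseline is a normal design, and the size of the gain is not known. The 88% needs all change variance to be visit noise, with independent errors. At a quarter noise the gain is 2.6 points. The starting 77.6% is itself uncertain, since the effect rests on this basis: "Preliminary studies with three healthy test subjects showed statistical data that indicated that the minimum number of subjects for this study is 18". The number of walks per evaluation is not stated, so the pretest's error is unknown. All of this stands. It limits the claim about size, but averaging still helps whenever visit noise is present and not perfectly correlated between the two visits.

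A reader might infer that using the pretest to choose the foot biases the main result through regression to the mean. The documents do not support that: the outcome is described as a magnitude, and the foot is chosen on several gait parameters. A reader might also infer that enrolment selects high pretest readings. Section 5 requires gait asymmetry but sets no threshold, and the plan does not say that the pretest confirms it.

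Nor is it right that the plan has no pair of tests without treatment between them. The follow-ups from one week to twelve months are such pairs, although they mix test-retest variation with loss of effect, and some participants may continue treatment.

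The new check is weak too. It covers about a week against at least four weeks of treatment, follows the shoe fitting, and has a wide interval. It cannot replace a control group.

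Finally, the measure at the start of treatment may already be a device-off walk. If so, only its definition and its use as baseline are missing.

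**Conclusion.** The point holds as a cheap improvement in precision, not as an error in the plan. Under a two-sided 5% paired t-test, effect 0.68, n = 18 and independent visit errors, a second device-off baseline raises power from 77.6% to about 80%, 83% or 88% for noise shares of 25%, 50% and 100%. The gain is smaller if errors correlate and nil if there is no visit noise. These figures describe the pre/post contrast that was powered, not the full ANOVA, and the true gain cannot be found from the documents.

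The change from pretest to session 1 is worth reporting but would expose only large drift. Regression to the mean should be raised only conditionally: if the pretest confirms the asymmetry criterion, or if asymmetry is signed by the side chosen at the pretest.

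**What to change.** In section 3:

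1. At session 1, before the device is put on, record the same short device-off walk as at the pretest, with the sensors already in use.
2. In the main analysis, use the mean of the two pre-treatment values as baseline. Score asymmetry at each visit first and then average; taking the magnitude of an averaged signed value could understate baseline asymmetry.
3. State whether the measure listed for the start of treatment is this device-off walk or a separate one.
4. Report the change from pretest to session 1 with its 95% confidence interval, labelled descriptive.
5. State whether asymmetry is analysed as a magnitude or a signed value, and whether the pretest confirms the entry criterion. If it is signed, or the pretest confirms entry, add a sensitivity analysis with session 1 alone as baseline. Averaging halves that bias, and the session-1 value is free of it if visit errors are independent.

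The cost is a few minutes of walking at a visit that already takes place, plus a few sentences of text. The walk must fit within the one-hour session limit, of which about 30 minutes is device treatment. The text should also say how it counts against the once-weekly limit on evaluations.
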